1.3 Exploratory analyses

Exploratory analyses will be described later, in separate SAP or in addenda to this SAP. Note that in the sister trial in Burkina Faso ("iLiNS-ZINC"), there is a pre-planned exploratory analysis: description of child feeding practices and factors associated with these practices including food security and seasonality, and relation with nutritional status (growth, iron status, morbidity).

3. Hypotheses to be tested

Stated qualitatively: Provision of LNS would not impact infant and young child feeding practices. More specifically, provision of LNS would not cause a change in:

- Breastfeeding (prevalence of any breastfeeding several time points throughout intervention, and reported frequency of breastfeeding the previous day)
- Frequency of feeding other solids foods (meals and snacks, or feeding episodes)²;

²These data are not yet available and variable construction and analyses are not described in this version.

- Dietary diversity measured as food group diversity at or above the WHO cut-off³;
- Number of nutrient-dense food groups (animal-source foods, fruits and vegetables)

4. Description of infant and young child feeding practice outcome variables

On the following pages, we present information on construction of outcome variables.

The table shows details on: data sources; variable names and variable construction; treatment of data and criteria for imputing missing values.

With few exceptions (detailed in the table) no data will be imputed for analyses of IYCF practices as outcomes.

However, in later analyses where longitudinal IYCF practice variables (e.g. indices summed across time points) may be used as potential effect modifiers, data could be imputed to avoid losing substantial numbers (those for whom data from all time points are not available).

Timing of outcomes: in the iLiNS-DOSE trial, target dates for collection of IYCF practices data were: Baseline (week 0, at ~5.5-6.5 mo of age); week 16; week 28; week 40; and endline (week 52). Data on breastfeeding practices, food group intake, and use of fortified products and vitamin/mineral drops were assessed at all time points. Data on frequency of meals and snacks were collected on KAP questionnaires at 6, 12, and 18 months of age (data not yet available).

³ WHO (2008) Indicators for assessing infant and young child feeding practices: conclusions of a consensus meeting held 6–8 November 2007 in Washington D.C., USA.

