5.4 Analysis of the effect of the intervention

General comments:

- a. The hypothesis stated in section 3 is a non-equivalence hypothesis. However, the study was not powered for IYCF practices outcomes and we are severely underpowered for equivalence analyses, particularly for dichotomous outcomes (such as prevalence of continued breastfeeding at any time point). Therefore the more traditional approach in the nutrition literature of analyzing for significant differences will be followed in the first instance. This limitation will be clearly explained in the discussion section of any publication.
- b. For quasi-continuous variables, we will supplement this with an equivalence approach to hypothesis testing, to help inform conclusions from this analysis.

Analysis of the effect of the intervention will follow these steps:

- a. A set of pre-specified potential covariates will be examined through reviewing correlations and collinearity (e.g. using "collin" command in Stata). Variables with VIF > 10 will be assessed and a reduced set of variables will be retained, such that all VIF are < 10.
- b. We will test the null hypothesis of no difference among the four treatment groups (iLiNS-DOSE) using ANCOVA or logistic regression, and controlling for the prespecified covariates (most of which are also potential effect modifiers, see below).
- c. For all analyses, if the global null hypothesis is rejected at 0.05 level, then we will perform post-hoc pairwise comparisons of all four groups using appropriate

adjustments for multiple comparisons and Scheffe's test to examine other contrasts of interest.

- d. The effects of potential effect modifiers will be assessed with an interaction term in the ANCOVA or logistic regression model. Each interaction will be assessed separately.
- e. Significant interactions (p < 0.05) will be further examined with stratified analyses, estimation of separate regression lines, or estimation of adjusted means at key points of the covariate, in order to understand the nature of the effect modification.

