- f. For quasi-continuous outcomes (number of fruit/vegetable groups consumed yesterday; number of animal-source food groups consumed yesterday, and fruit/vegetable and animal-source food scores for last week) equivalence will be assessed based on defined margins. Margins for yesterday will be ±1.0 (one more or one fewer fruit vegetable group; one more or one fewer animal-source food group). For scores for last week, the margin will be ±5 points for the fruit/vegetable scores and ±4 for animal-source foods (~= a difference of one group/day in each).
- g. We will assess equivalence in the context of ANCOVA models, controlling for the same pre-specified covariates as noted above. Equivalence will be determined to exist if the 90% confidence interval for the difference between the means is entirely contained within the negative and the positive values of the equivalence margin.
- h. Confidence intervals will be adjusted for multiple comparisons.
- i. For each outcome, if results are inconclusive, all LNS groups will be combined and 2-group comparisons will be made, to improve power to detect differences.

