5.5 Covariates in main effects models

In theory, a variety of community-, household-, maternal-, and child-level characteristics could affect child feeding practices independently of the intervention. Data are available for the covariates listed below. All covariates are as measured at baseline, with the exception of child age. Since child age at each visit can vary, child age at time of measure will be included in models. Before making final decisions on inclusion of covariates, completeness of data for the covariates will be considered and covariates will be excluded if loss of sample size is judged too large.

- Month of study during which the child was enrolled
- Characteristics of households
 - o Location of household, or distance to market and distance to clinic

- Baseline HH food security (HFIA score)
- Baseline HH asset score
- o Baseline HH housing quality score
- o Baseline HH livestock assets score
- o Number of underfives in the HH, assessed at baseline
- Maternal education
- Child's characteristics
 - o Child age
 - o Child sex
 - Child length-for-age z-score (LAZ) at baseline
 - o Child weight-for-length z-score (WLZ) at baseline

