Number of infants at enrollment. For exclusive breastfeeding n is the number of infants who were less than 6 months of age at enrollment.

^b LNS=lipid-based nutrient supplement; the quantities indicated are the size of the infant's daily dose, delivered to the household [indicate weekly or bi-weekly].

^c Comparison between intervention groups; p-value for ANOVA (continuous and quasi-continuous variables) or chi-square test (categorical variables).

^d Exclusive breastfeeding defined based on negative responses to a series of questions on fluids, semi-solids and solids consumed yesterday.

^e Respondents were asked if the baby was breastfed yesterday and if so they were read the following options: Only at night; only 1 or 2 times during the day; about 3 to 5 times during the day; at least 6 times during the day.

^f Respondents were asked (yes/no) if the infant was given any of a list of fluids and semi-solids yesterday, and solid food consumption was determined using an open, guided recall of the previous day (qualitative 24-hour recall). Foods reported in the recall were circled and coded into groups.

	N^{a}	(missing)	Control	LNS ^b 10 g	LNS 20 g	LNS 40 g	All	P-value ^c
Frequency of breastfeeding ^d								
At ~ X.X mo ^e (%)								
None								
6+ times								
At ~ XX.X mo (%)								
None								
6+ times								
At ~ XX.X mo (%)								
None								
6+ times								
At ~ XX.X mo (%)								
None								
6+ times								

Table 4a. Frequency of breastfeeding yesterday, by intervention group

^a Number of infants not permanently lost to follow-up at each age/time point.

^b LNS=lipid-based nutrient supplement; the quantities indicated are the size of the infant's daily dose, delivered to the household [indicate weekly or bi-weekly].

^c Values presented are unadjusted prevalences. Statistical tests are for adjusted analyses: logistic regression, controlling for.....

^d Respondents were asked if the baby was breastfed yesterday and if so they were read the following options: Only at night; only 1 or 2 times during the day; about 3 to 5 times during the day; at least 6 times during the day.

^e Approximate age shown is median observed age. After enrollment, additional data collection time points for infant feeding practices were: 16 weeks, 28 weeks, 40 weeks, and 52 weeks of participation in the study.

Table 5a Infant diet quality yesterday: food group diversity & nutrient-dense food groups

	N ^a	(missing)	Control	LNS ^b	LNS	LNS	Δ11	P-

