	19	(missing)	Control	10 g	20 g	40 g	All	value ^c
Food groups consumed by the infant yesterday ^{d}								
At ~ X.X mo ^e (%)								
4+ food groups (WHO indicator ^f , %)								
No ASF ^g (%)								
Mean or median $\#$ ASF groups (of 5) ^h								
No fruits/vegetables (%)								
Mean or median # fruit/vegetable groups $(of 5)^{i}$								
At ~ XX.X mo (%)								
4+ food groups (WHO indicator, %)								
No ASF(%)								
Mean or median # ASF groups (of 5)								
No fruits/vegetables (%)								
Mean or median # fruit/vegetable groups (of 5)								
At ~ XX.X mo (%)								
4+ food groups (WHO indicator, %)								
No ASF(%)								
Mean or median # ASF groups (of 5)								
No fruits/vegetables (%)								
Mean or median # fruit/vegetable groups (of 5)								
At ~ XX.X mo (%)								
4+ food groups (WHO indicator, %)								
No ASF(%)								
Mean or median # ASF groups (of 5)								
No fruits/vegetables (%)								
Mean or median # fruit/vegetable groups (of 5)								

^a Number of infants not permanently lost to follow-up at each age/time point.

^b LNS=lipid-based nutrient supplement; the quantities indicated are the size of the infant's daily dose, delivered to the household [indicate weekly or bi-weekly].

^c Values presented are unadjusted means (SD) or medians (I-Q ranges) and prevalences. Decision on presenting means or medians will be made after examination of distributions. Statistical tests are for adjusted analyses; analysis of covariance and logistic regression, controlling for...

^d Respondents were asked (yes/no) if the infant was given any of a list of fluids and semi-solids yesterday, and solid food consumption was determined using an open, guided recall of the previous day (qualitative 24-hour recall). Foods reported in the recall were circled and coded into groups.

^e Approximate age shown is median observed age. After enrollment, additional data collection time points for infant feeding practices were: 16 weeks, 28 weeks, 40 weeks, and 52 weeks of participation in the study.

^f The WHO indicator sums seven food groups and a score of 4 or more of 7 is associated with higher nutrient density (WHO, 200X); the food groups are: 1) grains, roots and tubers; 2) legumes and nuts; 3) dairy products; 4) flesh foods; 5) eggs; 6) vitamin-A rich fruits and vegetables; and 7) other fruits and vegetables.

^g ASF=animal-source food.

^h The 5 ASF groups are: 1) organ meats; 2) other meat/poultry; 3) fish; 4) eggs; and 5) dairy.

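### Appendix 05, 5.5: an incomplete covariate costs either children or the covariate itself in the adjusted outcome tests, with no threshold; simple filling of baseline covariates would avoid both losses

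*SAP*

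**What the plan says.** Appendix 05, 5.5 lists the covariates: enrolment month; household location (or distances to market and clinic); food insecurity, asset, housing and livestock scores; number of under-fives; maternal education; and child age, sex, LAZ and WLZ. All are baseline measurements except child age, which is taken at the visit. On incomplete data it undertakes to look at how complete the covariates are and says that "covariates will be excluded if loss of sample size is judged too large". It gives no numeric limit and no other remedy.

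These covariates enter the main results. In 5.4, step b tests for a difference between the four dose groups by ANCOVA or logistic regression, "controlling for the prespecified covariates". Step g adds the equivalence assessment: "We will assess equivalence in the context of ANCOVA models, controlling for the same pre-specified covariates as noted above". The footnotes to the diet-quality tables state: "Statistical tests are for adjusted analyses; analysis of covariance and logistic regression, controlling for". The means, medians and prevalences printed beside those P-values are unadjusted, and the N column is defined as "Number of infants not permanently lost to follow-up at each age/time point".

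Section 4 of the appendix says that, with few exceptions, "no data will be imputed for analyses of IYCF practices as outcomes". That sentence introduces the table on how outcome variables are built.

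**The concern.** A covariate can reduce the sample only if children without it leave the model, so complete-case analysis is the implied default although it is not named. A randomised child whose feeding data were collected can then drop out of the difference test and the equivalence interval because one household score is absent. The listed exclusions in section 5 of the appendix concern visit timing, not covariates. If too many children would go, the alternative is to discard the covariate and its contribution to precision.

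Appendix 05, 5.4 says the trial was not powered for these outcomes and is severely underpowered for equivalence, so avoidable loss of precision matters here. The completeness rule has no cut-off, whereas the collinearity rule in step a has one (VIF 10). Nor would a reader see how many children each P-value rests on: N counts infants not permanently lost, and nothing says that the missing column counts missing covariates.

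**Working it through.** The appendix states no power, sample-size or missingness figure for these analyses, so there is nothing to reproduce. All rates below are assumptions.

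**Inputs.** Covariates: 1 (month) + 1 or 2 (location) + 5 (household scores and under-fives) + 1 (maternal education) + 4 (child) = 12 or 13. Enrolled: 1932 (main SAP, section 2), which is 322 per original arm if allocation was equal.

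**1. Loss from complete-case modelling.** With k independent sources of missingness, each at rate m, the retained fraction is f = (1 − m)^k. The standard error (SE) rises by 1/√f − 1. A comparison with 80% power on all children has power Φ(2.80√f − 1.96) afterwards.

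The central illustration is three blocks. Household scores are likely to be missing together, LAZ and WLZ share one length measurement, and maternal education is the third block. Sex, enrolment month and age should be known for any enrolled, visited child.

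| Pattern | m | Lost (1 − f) | SE rise | Power from 80% |
|---|---|---|---|---|
| 3 blocks | 1% | 2.97% | 1.5% | 79% |
| 3 blocks | 2% | 5.88% | 3.1% | 78% |
| 3 blocks | 3% | 8.73% | 4.7% | 76% |
| 12 independent | 1% | 11.4% | 6.2% | 75% |
| 12 independent | 2% | 21.5% | 12.9% | 70% |
| 12 independent | 3% | 30.6% | 20.1% | 65% |

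Example: 0.97³ = 0.9127, so 8.73% are lost, and 1/√0.9127 = 1.047. At the other extreme, if the same children lack every covariate, the loss is just m: at 1-5%, power stays at 78-80%.

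**2. Cost of dropping covariates instead.** If the dropped covariates explain a share R² of outcome variance, the SE rises by 1/√(1 − R²) − 1. For R² = 0.05, 0.10, 0.20 and 0.30 that is 2.6%, 5.4%, 11.8% and 19.5%, and 80% power falls to 78%, 76%, 71% and 65%.

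**3. Filling compared with both routes.** This was a simulation of 4000 runs with a linear model, 322 against 322 children, nine covariates each 3% missing independently, and total R² 0.20:

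| Handling | Empirical SE | Power |
|---|---|---|
| No missing data | 0.0702 | 0.794 |
| Complete case | 0.0814 | 0.670 |
| All covariates dropped | 0.0777 | 0.707 |
| Overall-mean filling | 0.0705 | 0.793 |

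Bias was about zero in all four (between −0.0015 and −0.0012). Filling gives up about 0.4% in SE (0.0705/0.0702), against 16% and 11% for the other two. The missingness assumed here is heavier than in the three-block case, so the run shows the ordering of the methods, not the expected size of the loss.

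**The case against.** The strongest reply is that harm is not shown. The appendix says data are available for these covariates, no missing rates are given, and complete-case ANCOVA with a completeness check is common practice. The large-loss scenarios are also those in which the rule would drop the covariate, and in a randomised comparison with a linear model that costs precision without adding bias. This stands as a limit on size. It does not remove the point, because both permitted routes lose precision and a cheap alternative loses almost none.

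A reader might infer more than the text supports:

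- **Every test in the appendix is affected.** No. Table 3 uses ANOVA or chi-square, and attrition in 5.2 is tested by chi-square. Only the post-baseline treatment-effect tests are adjusted.
- **Covariates are chosen on results.** No. Completeness can be judged without looking at the outcome or the group effect. Step a already treats the list as potential covariates to be reduced, and the appendix adopts the main plan's scrambled-code procedure. What remains is an undefined cut-off.
- **Section 4 forbids filling covariates.** It concerns construction of outcome variables and sets no covariate rule.
- **The losses can be counted out of 1932.** Section 5 reports a substantial number of missed visits, so fewer children are available at any visit. Percentages are safer.
- **The tables conceal missing data.** They carry a missing column, and section 5 promises the number used when an outcome is missing for more than 10%. Neither is said to cover covariates, so only the narrower reporting gap remains.

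A blanket promise to retain all listed covariates would conflict with the VIF reduction and with the either/or location item. The remedy has to allow for both.

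**Conclusion.** The point holds as a cheap improvement to a secondary-outcome analysis; it is not an error that invalidates it. The only handling stated for an incomplete covariate is to lose the child from the adjusted post-baseline tests or, at an unstated point, to drop the covariate. With three blocks of missingness at 1-3% each, the cost is about 3-9% of children and 1.5-5% in standard error. It could be smaller if missingness is rare or falls on the same children. The 11-31% loss from 12 independently missing covariates is an upper bound and should not be read as the expected loss.

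The case for filling rests on randomisation: baseline covariates are independent of group, so values filled without using group or outcome do not bias the linear comparison. The simulation covers linear models only and does not establish the same for the logistic models.

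**What to change.** Replace the exclusion sentence in Appendix 05, 5.5 with:

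> Covariates remaining after the VIF step and the choice of location measure are not dropped for incompleteness. A missing baseline covariate is set to the overall sample mean (or modal category), computed without use of group or outcome, with a missing-value indicator if more than 5% are missing, so that every child with the outcome enters the main-effects model. This applies to baseline LAZ and WLZ as covariates only and does not alter the rule against imputing growth outcomes. Effect-modifier (interaction) tests use observed values of the modifier.

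The LAZ/WLZ clause keeps the text compatible with main SAP section 12.2, and the last sentence keeps filled values of a modifier out of the tests planned in 5.6. Child age at the visit needs no filling, since it should be known whenever the visit took place.

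In the outcome tables, report the number of children modelled beside each adjusted P-value.

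Cost: these sentences, a few lines of code and one table column. Adjustment is slightly less complete for the filled children, and in the logistic models the adjusted odds ratio may shift slightly.

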5.6 List of potential effect modifiers to be examined

Similarly most of the covariates identified above could interact with the provision of LNS to produce differential effects on feeding practices. Specifically, the household, maternal, and child-level characteristics, but not the temporal variable, will be evaluated for their potential to interact with intervention group.

5.7 Future exploratory (path) analyses

There are a number of potential effect modifiers not yet available, but which could interact with provision of LNS to produce differential effects. These may be included in later exploratory analyses:

- Household
 - Proxy for income (expenditures)
 - o Grandmother lives on compound/with the child
- Maternal
 - o Index for responsive feeding (composite from KAP)
 - o Maternal decision-making power (composite from KAP)
 - o Maternal depression
- Child
 - o Morbidity

o Appetite

7. Design of tables and figures

See following pages for a list of tables and example figures that will be examined by the manuscript writing group:

Table 1.	Number of observations and missing visits, by intervention group and by time point					
Table 2.	Background characteristics of study participants, baseline and endline samples, by intervention group					
Table 3.	Feeding practices at enrollment, by intervention group					
Table 4a.	Continued breastfeeding and frequency of breastfeeding yesterday, by intervention group					
(Table 4b.	Continued breastfeeding and frequency of breastfeeding yesterday, pairwise comparisons. This table, with pairwise comparisons, will be prepared if overall tests are significant)					
Table 5a	Infant diet quality yesterday: food group diversity & nutrient-dense food groups by intervention group					
(Table 5b	Infant diet quality yesterday: food group diversity & nutrient-dense food groups, pairwise comparisons. This table, with pairwise comparisons, will be prepared if overall tests are significant)					
Table 6a	Infant diet quality last week: nutrient-dense food groups, by intervention group					
(Table 6b	Infant diet quality last week : nutrient-dense food groups, pairwise comparisons This table, with pairwise comparisons, will be prepared if overall tests are significant)					
Example figures (final set of figures to be determined):						

Figure 1	Participant flow
Figure 2	Breastfeeding practices, by intervention group
Figure 3	Nutrient-dense food groups yesterday, by intervention group
Figure 4	Possibly, a Figure illustrating comparison between adjusted confidence intervals and equivalence margins

Table 1. Number of observations and missing visits, by time point (FFQ)

Age ^a	X.X mo			X.X mo			XX.X mo				XX.X mo				XX.X mo					
Group ^b	0	10	20	40	0	10	20	40	0	10	20	40	0	10	20	40	0	10	20	40
Number permanently																				
lost to follow-up																				
Number missing																				
% missing																				
Number completed																				
Total ^c																				

^a Median observed age. Infants were enrolled at 5.5-6.5 months of age. Subsequent data collection time points for infant feeding practices were: 16 weeks, 28 weeks, 40 weeks, and 52 weeks of participation in the study.

^b Group defined by assignment to receive 0 g LNS (control; delayed intervention); 10 g; 20 g; or 40 g.

^c Total number of children who should have been in data set at this time point (excluding permanent loss to follow-up).

LNS 20

All

P-value^b

LNS 40 g (missing) Control LNS^a 10 g Ν g Time of enrollment Baseline sample Endline sample Location of HH (or distances to clinic, market) Baseline sample Endline sample HFIA score at baseline Baseline sample Endline sample HH asset score at baseline Baseline sample Endline sample HH housing quality score at baseline Baseline sample Endline sample HH livestock assets score at baseline Baseline sample Endline sample Number of underfives in the HH at baseline Baseline sample Endline sample Maternal education (in y) Baseline sample Endline sample Child age at baseline (in mo) Baseline sample Endline sample Child sex (% female) Baseline sample Endline sample Child length-for-age z-score (LAZ) at baseline Baseline sample Endline sample

Table 2. Background characteristics of study participants

Child weight-for-length z-score (WLZ) at baseline

Baseline sample

Endline sample

^a LNS=lipid-based nutrient supplement; the quantities indicated are the size of the infant's daily dose, delivered to the household *[indicate weekly or bi-weekly]*.

^b Comparison between intervention groups at each time point; p-value for (describe tests).

Table 3. Feeding practices at enrollment, by intervention group

	\mathbf{N}^{a}	(missing)	Control	LNS ^b 10 g	LNS 20 g	LNS 40 g	All	P-value ^c
Exclusive breastfeeding, infants <6 mo ^d								
Frequency of breastfeeding ^e								
None								
6+ times								
Food groups consumed by the infant yesterday ^f								
Porridge								
Other grain-based foods or roots/tubers								
Any legumes or nuts								
Any dairy (liquids, semi-solids, solids)								
Any meat, poultry or fish								
Any eggs								
Any vitamin A-rich fruit and/or vegetable								
Any other fruit and/or vegetable								
^a Number of infants at enrollment. For exclusive breastfeed	ling n is t	he number of in	fants who w	ere less than 61	monthsofage	at enrollment		

Number of infants at enrollment. For exclusive breastfeeding n is the number of infants who were less than 6 months of age at enrollment.

^b LNS=lipid-based nutrient supplement; the quantities indicated are the size of the infant's daily dose, delivered to the household [indicate weekly or bi-weekly].

^c Comparison between intervention groups; p-value for ANOVA (continuous and quasi-continuous variables) or chi-square test (categorical variables).

^d Exclusive breastfeeding defined based on negative responses to a series of questions on fluids, semi-solids and solids consumed yesterday.

^e Respondents were asked if the baby was breastfed yesterday and if so they were read the following options: Only at night; only 1 or 2 times during the day; about 3 to 5 times during the day; at least 6 times during the day.

^f Respondents were asked (yes/no) if the infant was given any of a list of fluids and semi-solids yesterday, and solid food consumption was determined using an open, guided recall of the previous day (qualitative 24-hour recall). Foods reported in the recall were circled and coded into groups.

	N^{a}	(missing)	Control	LNS ^b 10 g	LNS 20 g	LNS 40 g	All	P-value ^c
Frequency of breastfeeding ^d								
At ~ X.X mo ^e (%)								
None								
6+ times								
At ~ XX.X mo (%)								
None								
6+ times								
At ~ XX.X mo (%)								
None								
6+ times								
At ~ XX.X mo (%)								
None								
6+ times								

Table 4a. Frequency of breastfeeding yesterday, by intervention group

^a Number of infants not permanently lost to follow-up at each age/time point.

^b LNS=lipid-based nutrient supplement; the quantities indicated are the size of the infant's daily dose, delivered to the household [indicate weekly or bi-weekly].

^c Values presented are unadjusted prevalences. Statistical tests are for adjusted analyses: logistic regression, controlling for.....

^d Respondents were asked if the baby was breastfed yesterday and if so they were read the following options: Only at night; only 1 or 2 times during the day; about 3 to 5 times during the day; at least 6 times during the day.

^e Approximate age shown is median observed age. After enrollment, additional data collection time points for infant feeding practices were: 16 weeks, 28 weeks, 40 weeks, and 52 weeks of participation in the study.

Table 5a Infant diet quality yesterday: food group diversity & nutrient-dense food groups

	N ^a	(missing)	Control	LNS ^b	LNS	LNS	Δ11	P-
	19	(missing)	Control	10 g	20 g	40 g	All	value ^c
Food groups consumed by the infant yesterday ^{d}								
At ~ X.X mo ^e (%)								
4+ food groups (WHO indicator ^f , %)								
No ASF ^g (%)								
Mean or median $\#$ ASF groups (of 5) ^h								
No fruits/vegetables (%)								
Mean or median # fruit/vegetable groups $(of 5)^{i}$								
At ~ XX.X mo (%)								
4+ food groups (WHO indicator, %)								
No ASF(%)								
Mean or median # ASF groups (of 5)								
No fruits/vegetables (%)								
Mean or median # fruit/vegetable groups (of 5)								
At ~ XX.X mo (%)								
4+ food groups (WHO indicator, %)								
No ASF(%)								
Mean or median # ASF groups (of 5)								
No fruits/vegetables (%)								
Mean or median # fruit/vegetable groups (of 5)								
At ~ XX.X mo (%)								
4+ food groups (WHO indicator, %)								
No ASF(%)								
Mean or median # ASF groups (of 5)								
No fruits/vegetables (%)								
Mean or median # fruit/vegetable groups (of 5)								

^a Number of infants not permanently lost to follow-up at each age/time point.

^b LNS=lipid-based nutrient supplement; the quantities indicated are the size of the infant's daily dose, delivered to the household [indicate weekly or bi-weekly].

^c Values presented are unadjusted means (SD) or medians (I-Q ranges) and prevalences. Decision on presenting means or medians will be made after examination of distributions. Statistical tests are for adjusted analyses; analysis of covariance and logistic regression, controlling for...

^d Respondents were asked (yes/no) if the infant was given any of a list of fluids and semi-solids yesterday, and solid food consumption was determined using an open, guided recall of the previous day (qualitative 24-hour recall). Foods reported in the recall were circled and coded into groups.

^e Approximate age shown is median observed age. After enrollment, additional data collection time points for infant feeding practices were: 16 weeks, 28 weeks, 40 weeks, and 52 weeks of participation in the study.

^f The WHO indicator sums seven food groups and a score of 4 or more of 7 is associated with higher nutrient density (WHO, 200X); the food groups are: 1) grains, roots and tubers; 2) legumes and nuts; 3) dairy products; 4) flesh foods; 5) eggs; 6) vitamin-A rich fruits and vegetables; and 7) other fruits and vegetables.

^g ASF=animal-source food.

^h The 5 ASF groups are: 1) organ meats; 2) other meat/poultry; 3) fish; 4) eggs; and 5) dairy.

ⁱ The 5 fruit and vegetables groups are: 1) vitamin A-rich orange/yellow vegetables; 2) dark green leafy vegetables; 3) other vegetables; 4) vitamin A-rich fruits; and 5) other fruits.

Table 5a Infant diet quality last week: nutrient-dense food groups, by intervention group

	N ^a	(missing)	Control	LNS ^b 10 g	LNS 20 g	LNS 40 g	All	P- value ^c
Food groups consumed by the infant in the last 7 days ^d					0			
At ~ X.X mo ^{e} (%)								
Mean or median ASF score $(of 28)^{g}$								
Lowest ASF tertile $(\%)^{h}$								
Mean or median fruit/vegetable score (of 35) ⁱ								
Lowest fruit/vegetable tertile (%)								
At ~ XX.X mo (%)								
Mean or median ASF score (of 28)								
Lowest ASF tertile (%)								
Mean or median fruit/vegetable score (of 35)								
Lowest fruit/vegetable tertile (%)								
At ~ XX.X mo (%)								
Mean or median ASF score (of 28)								
Lowest ASF tertile (%)								
Mean or median fruit/vegetable score (of 35)								
Lowest fruit/vegetable tertile (%)								
At ~ XX.X mo (%)								
Mean or median ASF score (of 28)								
Lowest ASF tertile (%)								
Mean or median fruit/vegetable score (of 35)								
Lowest fruit/vegetable tertile (%)								
^a Number of infants not permanently lost to follow-up at e	each ag	e/time point.						

^b LNS=lipid-based nutrient supplement; the quantities indicated are the size of the infant's daily dose, delivered to the household *[indicate weekly or bi-weekly]*.

^c Values presented are unadjusted means (SD) or medians (I-Q ranges) and prevalences. Decision on presenting means or medians will be made after examination of distributions. Statistical tests are for adjusted analyses; analysis of covariance and logistic regression, controlling for

^d Respondents were asked how many days in the last seven days the infant was given any of a list of foods. Foods were read to the respondent in groups. The respondent was also instructed to consider ingredients of mixed dishes.

^e Approximate age shown is median observed age. After enrollment, additional data collection time points for infant feeding practices were: 16 weeks, 28 weeks, 40 weeks, and 52 weeks of participation in the study.

^fASF=animal-source food.

^g The ASF score equals the sum, across four animal-source food groups, of the number of days in the last seven days the respondent reported the infant consumed a food in the group. The four groups are: 1) meat/poultry; 2) fish; 3) eggs; and 4) dairy. Scores could range from 0 to 28.

^h Tertiles are based on the full sample at each time point. The table shows the percent of children in each intervention group falling into the lowest tertile for the ASF score and for the fruit/vegetable score.

ⁱ The fruit/vegetable score equals the sum, across five fruit and vegetable food groups, of the number of days in the last seven days the respondent reported that the child consumed a food in the group. The five groups are: 1) vitamin A-rich yellow/orange vegetables; 2) dark green leafy vegetables; 3) vitamin A-rich fruits; 4) other fruits; 5) other vegetables. Scores could range from 0 to 35.

Figure 1

Figure 1 will present a detailed participant flow chart (CONSORT diagram). The Figure will include numbers and reasons for permanent and temporary loss-to-follow-up at each time point where outcomes are evaluated (visits at weeks 16, 28, 40, and 52).

Figure 2 Breastfeeding practices, by intervention group

Either bar or line graphs, with confidence intervals, will be used to present adjusted or unadjusted prevalences by intervention group and by time point. If relevant, the Figure legend will indicate covariates adjusted for. Data presented here are illustrative only (observations at each time point were randomly allocated to 4 groups).

Figure 3 Mean number of nutrient-dense food groups yesterday, by intervention group

Either bar or line graphs, with standard error bars, will be used to present adjusted or unadjusted means by intervention group and by time point. If relevant, the Figure legend will indicate covariates adjusted for. Data presented here are illustrative only (observations at each time point were randomly allocated to 4 groups).

Panel A – Animal-source food groups

Prevention of Linear Growth Faltering in Infants and Young Children With Lipid-based Nutrient Supplements (iLiNS-DOSE)

Statistical Analysis Plan

Appendix 06: Hypothetical Willingness-to-Pay for LNS and Likuni Phala at Baseline (added on 23.04.2014)

Contents

1.	Brief Introduction and Motivation
2.	Description of Variables
